9.4 Interim Analyses and Stopping Rules

No interim analyses are planned. The study PI will periodically review video recordings of visit interventions as the study progresses to offer feedback to the study intervention providers and ensure adherence to the protocol.

If at any point 20% or more of participants have dropped from the study due to adverse effects from amitriptyline or omeprazole and/or there is a serious adverse event likely due to amitriptyline or omeprazole, the study team will meet with the study safety monitor to determine whether any protocol modifications are necessary.

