3. STUDY DESIGN

Study design: Single-center, single-blind, randomized controlled trial

Primary outcome:

1. Change in the average daily GERD symptom severity score from baseline to the last week of the study in the expanded vs. standard group. GERD symptom severity is based on the sum of scores assessing the severity of daytime heartburn, nighttime heartburn, and acid reflux each on a 0-4 point scale (none, mild, moderate, severe, very severe; higher scores signify worse symptoms).

Secondary outcomes:

1. Ratio of the sum of positive correlations over the sum of negative correlations in GSR (or HRV) across patient-provider encounters for standard vs. expanded visit types and for responders vs. non-responders (those with a 50% or greater improvement in their GERD symptom severity).
2. Absolute change in GSR (or high frequency HRV signal) in patient recordings from the beginning of the study visit to the end of the study visit and correlation with subsequent change in GERD symptom severity.
3. Differences in blinded ratings of 2 minute thin slices of study visit videos from the beginning to the end of the study in supportive global impressions (e.g., engagement, relaxed, patient seems pleased/satisfied) and non-verbal behaviors (e.g., smiling) between standard and expanded visit types and correlation with subsequent change in GERD symptom severity.

Study population:

Men and women age 24-70 with heartburn symptoms 3 or more days per week not responsive to proton pump inhibitors or with known functional heartburn. We will enroll until we reach 60 completing subjects.

Study location:

University of California Davis Medical Center

Length of subject participation: 8 weeks

Length of study enrollment: 2 years

Groups:

- 1) Standard visit (n=30), modeled after an empathic, high quality conventional primary care visit.
- 2) Expanded visit (n=30), modeled after a visit with an integrative medicine provider

Randomization:

The randomization code will be generated by the study statistician as described below (sections 4.3 and 9.2). The study will be single-blinded (study providers and the research team will know what the subject is receiving but the subject will not). Randomization will be stratified based on study provider. We anticipate 5 or 6 providers each seeing 10-12 subjects (5-6 standard visits, 5-6 expanded visits).

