- Amitriptyline: The most common side effects are dry mouth, sleepiness, and constipation. Less common side effects include dizziness, fatigue, headache, agitation, tremor, blurred vision, nausea, insomnia, and sexual dysfunction. Rare side effects include an allergic reaction, changes in heart conduction causing slowing or speeding up of the heart rate, serotonin syndrome, and suicidal ideation. We are prescribing low doses of this medication and have excluded those most vulnerable to adverse effects and so do not anticipate any serious adverse events. If a study subject calls with concerns about side effects, they will be directed to speak with a physician on the study team to assess their symptoms and determine whether any dose modification or further evaluation is needed. If it is deemed that the subject should stop the medication, they will be instructed in how to do so. If it is determined that they need further medical evaluation, they will be instructed what to do.
- Omeprazole: The most common side effects are headaches, abdominal pain, diarrhea, and nausea. Less common side effects include skin rash, constipation, dizziness, and back pain. Rarely someone may develop a hypersensitivity reaction, acute interstitial nephritis, lupus, or an enteric infection. Long-term use may increase the risk of

fractures, vitamin B12 deficiency, or low magnesium levels. Despite these risks, omeprazole is generally well-tolerated and available over-the-counter. If a study subject calls with concerns about side effects, they will be directed to speak with a physician on the study team to assess their symptoms and determine whether any dose modification or further evaluation is needed. If it is deemed that the subject should stop the medication, they will be instructed in how to do so. If it is determined that they need further medical evaluation, they will be instructed what to do.

- Severe GERD symptoms: It is possible that subjects may experience a flare in their GERD symptoms during the study. If a subject calls with severe GERD symptoms, he or she will be directed to speak with a study physician to discuss their symptoms and determine the best course of action. In some cases as needed antacids may be recommended for refractory symptoms. If this recommendation does not suffice, the subject may need to initiate additional medication and possibly be removed from the study.

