9.2 Sample Size and Randomization

The combined standard deviation (root mean square error) in my pilot fellowship study was 1.5⁶⁴. We are conservatively assuming that this number will likely be larger in this study given the greater number of providers involved. Given 30 subjects in each group (n=60 total), 80% power, a two-sided significance test with alpha = 0.05, the minimal detectable difference (MDD) in GERD symptom severity scores between the standard and expanded groups given the estimated standard deviations (SD) is shown in the adjacent table. These MDD values are similar to those found in my fellowship study⁶⁴ and are clinically meaningful^{86,87}.

Minimal Detectable Difference Between Groups	
SD	MDD
1.5	1.10
2.0	1.47
2.5	1.84

Treatment Assignment Procedures

A randomization scheme will be devised before the start of the study by the study biostatistician who will retain the code and will be responsible for breaking the blind at the end of the study. We do not anticipate a need to break the blind during the study because we are not expecting serious adverse events to occur more frequently in one visit group than another. Randomization will be stratified by provider, with permuted block sizes of 2 and 4 with a goal to have 5-6 providers each see 10-12 subjects. If a provider cannot commit to this many visits, the study biostatistician may need to adjust the randomization scheme and we will consent additional providers.

The study biostatistician will enter the randomization scheme into REDCap and subjects will be randomized immediately prior to the study visit intervention.

If a subject drops out or is unable to complete the study, the statistician may need to rebalance the randomization scheme.

Subjects will be informed of their visit group assignment during the debriefing at the end of the second study visit.

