Appendix B: Screening Documents

- B.1 Telephone script for pre-screening (amitriptyline substudy)
- B.1.1 Telephone script for pre-screening (omeprazole substudy)
- B.2 Screening form
- B.3 COVID-19 Screening

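### The 20% dropout trigger in section 9.4 pools two drugs, so the single-drug dropout rate needed to prompt a safety review depends on an unplanned drug split

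*Combined protocol and SAP*

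**What the plan says.** Section 9.4 plans no interim analysis but sets a safety-review trigger with two limbs. The first is "If at any point 20% or more of participants have dropped from the study due to adverse effects from amitriptyline or omeprazole". The second follows in the same sentence: "and/or there is a serious adverse event likely due to amitriptyline or omeprazole". If either is met, "the study team will meet with the study safety monitor to determine whether any protocol modifications are necessary". No denominator, minimum number of subjects or per-drug count is given.

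Elsewhere the plan treats the two drug groups separately. Sections 4.1 and 4.2 give each its own eligibility lists, and section 7.1 adds exclusions for amitriptyline alone. Appendix B lists one pre-screening script per drug and labels each a substudy, the first as "Telephone script for pre-screening (amitriptyline substudy". Section 7 describes different risks. For amitriptyline, "Rare side effects include an allergic reaction, changes in heart conduction causing slowing or speeding up of the heart rate, serotonin syndrome" and suicidal ideation are named. By contrast, "omeprazole is generally well-tolerated and available over-the-counter".

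The Précis assigns the drug by type of symptom. Sections 3 and 9.2 stratify randomisation by provider only. No target or cap per drug is stated.

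**The concern.** A fraction meant to detect poor tolerability should divide those harmed by those exposed. Here the numerator may come from one drug while the denominator counts takers of both. The single-drug rate that prompts a review is then set by the recruitment mix, not by a decision about how much dropout is acceptable. A tolerability problem confined to the less-used drug could continue for some time, or to the end of enrolment, without this limb bringing the study team and the monitor together.

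The point is limited to adverse effects that make people leave but are not serious. A single serious event likely due to either drug meets the second limb, whatever the split.

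**Working it through.** Section 9.4 states no operating characteristics, so there is no figure of the plan's own to reproduce.

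**Inputs from the documents.** Threshold 20% (9.4). Planned size 60: "Given 30 subjects in each group (n=60 total), 80% power, a two-sided significance test with alpha = 0.05" (9.2).

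**Assumptions.** The documents give neither the drug split nor dropout rates. I take 15 to 50 of 60 subjects on amitriptyline, with true adverse-effect dropout of 30% on amitriptyline and 3% on omeprazole.

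**Step 1: rate needed on one drug.** The count needed is 0.20 × 60 = 12. With nA subjects on the affected drug and no dropouts on the other, the required rate is 12/nA. For example, 8 dropouts among 20 is 40% on that drug but 8/60 = 13.3% pooled, which does not reach the limb. With fewer than 12 subjects on a drug, the limb cannot be met at 60 from that drug alone.

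**Step 2: one look at 60 subjects.** The pooled probability is the sum over a of P[Bin(nA, 0.30) = a] × P[Bin(60 − nA, 0.03) ≥ 12 − a]. The within-drug probability is P[Bin(nA, 0.30) ≥ 0.2 nA], that is at least 3, 4, 6, 8, 9 or 10 dropouts for nA = 15, 20, 30, 40, 45 or 50.

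**Step 3: running check.** The limb applies at any time, so I also computed the exact probability that the pooled fraction ever reaches 20%. Subjects enter in random order and each dropout is counted at entry. That simplification favours early firing.

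| On amitriptyline | Rate needed | Pooled, once at 60 | Pooled, running from 1st subject | Pooled, running from 20th | Within amitriptyline, once at full enrolment |
|---|---|---|---|---|---|
| 15 | 80% | 0.01 | 0.49 | 0.15 | 0.87 |
| 20 | 60% | 0.04 | 0.60 | 0.28 | 0.89 |
| 30 | 40% | 0.27 | 0.80 | 0.60 | 0.92 |
| 40 | 30% | 0.64 | 0.92 | 0.84 | 0.94 |
| 45 | 27% | 0.78 | 0.96 | 0.91 | 0.95 |
| 50 | 24% | 0.88 | 0.98 | 0.96 | 0.96 |

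Like for like, a within-amitriptyline fraction checked from its first subject ever reaches 20% with probability about 0.94, 0.96 and 0.98 for 15, 20 and 30 subjects (100,000 simulated trials).

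**Step 4: other rates.** At 40% and 2%, the pooled limb at 60 is met with probability 0.02, 0.13, 0.65 and 0.94 for 15, 20, 30 and 40 on amitriptyline. The within-drug figures are 0.97 to 1.00.

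**Step 5: replacement of dropouts.** Section 3 says "We will enroll until we reach 60 completing subjects". If everyone enrolled counts, the threshold becomes 15 of 75 (15/75 = 20%). The dilution has the same form.

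**Step 6: chance firing of a within-drug rule.** With 20 subjects on a drug, at least 4 dropouts occur with probability 0.02 at a true 5% and 0.13 at a true 10%. On a running check from the first subject these become about 0.25 and 0.49. Most of that is one dropout among the first five: 1 − 0.95^5 = 0.23 and 1 − 0.90^5 = 0.41. Checked from the 10th subject, taken only as an example, they are about 0.10 and 0.31. The present pooled rule, checked from the first of 60 subjects at the same true rates on both drugs, gives about 0.25 and 0.50.

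**The case against.** The strongest reply is that the rule as written is not a single look at 60. It applies throughout, and on a running check it often fires even when the affected drug is in the minority. That stands, and it rules out reading the pooled limb as unable to detect a one-drug problem. Part of the early firing is instability in tiny denominators, however, and checked from the 20th subject the gap is still wide for 30 or fewer on amitriptyline.

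Second, sections 1.1 and 3 and the Précis describe a largely functional or PPI-unresponsive population, which may put most subjects on amitriptyline. With 40 to 50 of 60 on it, dilution is modest. That also stands. But section 4.1 opens a separate omeprazole route, section 4.3 recruits patients who have not yet tried a PPI, and nothing fixes the mix.

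Third, a reader might infer that the conduction, serotonin-syndrome and suicidality risks would go unreviewed. The documents do not support this. When serious and likely drug-related, one such event meets the second limb.

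Fourth, a reader might infer that this is the only safeguard against non-serious harm. That cannot be established. Section 7.6 refers to a monitoring plan in Appendix G, which was not in the text reviewed, and section 7.3 sends the independent monitors an annual adverse-event summary. An annual summary is slow beside an 8-week exposure, but it is a second route.

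**Conclusion.** The concern holds for the 20% limb. It is pooled over two differently screened groups, and the single-drug rate needed to reach it at 60 subjects runs from 24% to 80% as the affected group falls from 50 to 15. The loss of sensitivity is large when about 20 or fewer subjects take the affected drug, material at 30, and small at 45 to 50. All probabilities rest on assumed splits and dropout rates and on how the any-time wording is applied.

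A related ambiguity affects the numerator. Section 8 keeps subjects who stop the drug for an adverse reaction in follow-up unless they decline, while 9.4 counts those who have dropped from the study. Whether the former count is not stated, and the two sections must be reconciled.

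The consequence of the trigger is a meeting. Type I error, power and the comparison of visit types are unaffected. The change is worth making because it is cheap, not because the trial's main result depends on it.

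**What to change.** In section 9.4, keep the sponsor's 20% and the meeting with the safety monitor, but assess the fraction separately among participants dispensed amitriptyline and among those dispensed omeprazole. Define the denominator as the number dispensed that drug to date. State a minimum number dispensed, chosen by the sponsor, before the fraction is assessed. Leave the serious-event limb as it is. State consistently in sections 8 and 9.4 whether a subject who stops the drug for an adverse reaction but stays in follow-up is counted. If Appendix G already monitors by drug, cite it in 9.4.

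The cost is a few sentences and a tally by drug in the adverse-event log that section 7.4 already requires. Smaller denominators bring more chance firings, as in step 6. The minimum number limits these, and each costs only a meeting. The present pooled rule, checked from the first subject, has much the same early chance firing.

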6.2.6 Telephone Check-in

Study coordinators will call enrolled subjects who have completed study visit 1 twice to check in. The first time will be approximately 1 week after the first study visit and the second time 1 week before the second study visit. These telephone check-ins will 1) serve as a reminder to participants to complete their daily symptom diary, 2) remind participants to take the medication as prescribed 3) address any participant questions or concerns, and 4) remind/confirm participants’ second study visit appointment.

Participants who wish to discontinue the study medication and unenroll from the study will be directed to speak with the study PI to receive instructions for tapering off of the medication if they have not done so already.

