7.3 Adverse Events and Serious Adverse Events

An **adverse event (AE)** is any unfavorable or unintended diagnosis, symptom, sign, syndrome or disease which either occurs during the study (having been absent at baseline), or if present at baseline, appears to worsen.

A **serious adverse event (SAE)** is any untoward medical occurrence that results in death, is life threatening, requires inpatient hospitalization or prolongation of existing hospitalization, results in persistent or significant disability/incapacity, or is a congenital anomaly.

During the follow-up visit, the study team member will specifically ask about any new or worsening symptoms in the last 8 weeks, unanticipated medical appointments, emergency room, or hospital visits.

In addition, during telephone check-ins, the study research coordinator will record any health concerns reported by subjects (not specifically solicited) and report these to the study PI. If there are any signs or symptoms of concern or that require further clarification, the study PI will contact the subject.

- Unexpected fatal or life-threatening AEs related to the intervention will be reported to the National Center for Complementary and Integrative Health (NCCIH) Program Officer within 3 business days of the investigator becoming aware of the event and to the study's Independent Safety Monitor(s) and UC Davis IRB within 5 business days of the investigator becoming aware of the event. Other serious and unexpected AEs related to the intervention will be reported within 5 business days.
- Anticipated or unrelated SAEs will be handled in a less urgent manner but will be reported to the Independent Safety Monitor(s), IRB, and other oversight organizations in accordance with their requirements and will be reported to NCCIH on an annual basis.
- All other AEs documented during the course of the trial will be reported to NCCIH and the UC Davis IRB on an annual basis by way of inclusion in the annual report and in the annual AE summary which will be provided to NCCIH and to the Independent Monitors. The Independent Safety Monitor(s) Report will state that all AEs have been reviewed (see Data Safety and Monitoring Plan).

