7.4 Reporting Procedures

Study staff and visit intervention providers will be instructed to report all adverse events (or potential AEs) to the study PI ([name]). Determination of relatedness will be made in conjunction with [name] and/or [name]. An electronic log of various types of AEs will be kept and updated by study staff.

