8. INTERVENTION DISCONTINUATION

Subjects who decline to participate in study procedures (e.g., completion of study questionnaires, physiologic monitoring, and/or video recording) will be terminated from the study without further follow-up. Any subjects who are disruptive or felt to pose a threat to study staff will also be terminated without follow-up. If a subject experiences an adverse reaction to amitriptyline or omeprazole and decides to stop taking the medication, or if a study physician deems it in the subject's best interest to stop the medication, the subject will continue to be followed for the duration of their initially planned participation (out to 8 weeks), unless the subject declines to participate further.

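### The 20% condition in the Section 9.4 safety trigger counts participants who leave the study, so those who stop the drug for a non-serious adverse effect and stay in follow-up are missed

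*Combined protocol and SAP*

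**What the plan says.** Section 9.4 (Interim Analyses and Stopping Rules) has two conditions joined by and/or. The first is a rate: "If at any point 20% or more of participants have dropped from the study due to adverse effects from amitriptyline or omeprazole". The second is a single event: "and/or there is a serious adverse event likely due to amitriptyline or omeprazole". Either leads to the same action: "the study team will meet with the study safety monitor to determine whether any protocol modifications are necessary".

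Section 8 (Intervention Discontinuation) says what happens to someone who stops amitriptyline or omeprazole after an adverse reaction, whether by the subject's own decision or a study physician's. That person "will continue to be followed for the duration of their initially planned participation (out to 8 weeks), unless the subject declines to participate further".

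Section 6.2.6 (Telephone Check-in) mentions "Participants who wish to discontinue the study medication and unenroll from the study", which names the two acts side by side. Section 3 adds that "We will enroll until we reach 60 completing subjects", so those who leave are replaced. Section 9.4 gives no denominator for its 20%.

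**The concern.** The rate condition depends on leaving the study, while Section 8 makes staying in the study the normal course for someone who has stopped the drug. A poorly tolerated drug could therefore be stopped by 20% or more of participants without the condition being met. The better the study retains these subjects, the less likely the condition is to be met.

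The effects at issue are the ordinary ones. Section 7 lists dry mouth, sleepiness and constipation as the most common effects of amitriptyline. These can make a subject stop without meeting the definition of a serious event in Section 7.3, so the second condition would not respond. At stake is a prompt, independent look at tolerability across participants. Without the trigger, Section 7.3 sends other adverse events to the independent monitors "in the annual AE summary which will be provided to NCCIH and to the Independent Monitors", which is slow beside 8 weeks on drug and 2 years of enrolment.

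**Working it through.** **Text.** Section 8 carries the point: the default status after a drug stop is continued follow-up. Section 9.2 uses the same verb, dropping out, for leaving the study. Section 7 discusses stopping the drug for side effects without mentioning removal; it mentions possible removal only for severe GERD symptoms that need additional medication. No supplied section extends dropping from the study to a drug stop with continued follow-up.

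**Simple example.** The plan gives no derivation for its 20%, so there is no figure to reproduce. Of 60 participants, 20% is 0.20 × 60 = 12. Suppose 18 stop for non-serious effects and 9 of them stay. As written the count is 9/60 = 15%, and no meeting is called. Counting all stops gives 18/60 = 30%, and one is.

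**Chance of a trigger.** Inputs:
- From the documents: the 20% threshold, applied at any point with no minimum (9.4), and 60 participants (Sections 3 and 9.2).
- Assumed: stop rate p for non-serious adverse effects; share s of stoppers who also leave; a running denominator of participants started to date; independence between participants; no delay between starting and stopping.

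Each participant is counted with probability q = p × s under the current text, and q = p if all drug stops count. Let f(n, k) be the probability that k of the first n are counted and no trigger has yet occurred. Then f(n, k) = f(n−1, k)(1−q) + f(n−1, k−1)q for k < 0.20n, and any path reaching k ≥ 0.20n is a trigger. The chance of a trigger is 1 minus the sum of f(60, k) over k.

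| Stop rate p | Drug stops count | As written, 75% leave | 50% leave | 25% leave | None leave |
|---|---|---|---|---|---|
| 5% | 0.25 | 0.19 | 0.125 | 0.06 | 0 |
| 10% | 0.50 | 0.375 | 0.25 | 0.125 | 0 |
| 20% | 0.90 | 0.73 | 0.50 | 0.25 | 0 |
| 30% | 0.996 | 0.95 | 0.73 | 0.375 | 0 |

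If all stoppers leave, s = 1 and the two columns coincide.

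Much of the chance at low rates arises early, because one counted person among the first five already makes 1/5 = 20%. At q = 0.10 that alone gives 1 − 0.9^5 = 0.41 of the 0.50.

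**Other denominators.** Running the same recursion until 60 participants have not left changes no entry by more than 0.01. With one look at a fixed 60 and X ~ Binomial(60, q), P(X ≥ 12) at p = 20% is 0.55 if all stops count and 0.015 as written with half leaving; at p = 30% it is 0.97 against 0.18. At p = 10% even counting every stop gives only 0.015. A fixed 60 does not match replacement of leavers: with 60 completers, 12 leavers are 12/72 = 16.7%, and 15/75 are needed for 20%. The level depends heavily on the denominator; the direction of the gap does not.

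**The case against.** **Appendix G.** Section 7.6 refers safety monitoring to a separate plan in Appendix G, which was not supplied and may define the count. This stands as a limit: the point is about the sentence in 9.4, which neither cites nor defers to that appendix. A reader might infer that the trial counts drug stops nowhere; the documents do not show that.

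**Loose wording.** The team may use dropped for anyone who stops the drug. The phrase in Section 6.2.6 joins stopping and unenrolling for one group of subjects, and could be read as treating them as one step. It is weak evidence either way. Section 8 is explicit, and it supports the literal reading.

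**Other oversight.** Staff and providers are "instructed to report all adverse events (or potential AEs) to the study PI", and a running log is kept (7.4). The investigator reviews logs at least every 1–2 months (10.3.3), a call at about one week checks that the drug is being taken (7.2), and subjects who call about side effects speak with a study physician (7). A cluster of stops could well be noticed before the annual summary, and nothing bars an ad hoc meeting. This reduces the weight, but none of it obliges the team to bring the safety monitor in at a given rate.

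**Stronger reading.** One might infer that a stopping rule is disabled or that subjects are unprotected. The text does not support this: the action is a meeting, individual care does not depend on the rate, and a related serious event has its own condition.

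**Assumed inputs.** Stop rates, leaving shares and the denominator are not in the documents. The table illustrates the gap; it does not predict this trial.

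**Conclusion.** The gap in the wording of 9.4 is real and small. Non-serious drug stops that remain in follow-up are not counted, so the 20% condition can stay silent when 20% or more have stopped the drug. The loss grows with the share of stoppers retained, from none if all leave to complete if none leave. The consequence is a missed or late meeting about non-serious tolerability. Power and the primary analysis are not affected. Confidence is medium, mainly because Appendix G could not be read. This is a cheap improvement to consider.

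**What to change.** Reword the first condition of 9.4 along these lines:

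> *At any point, 20% or more of the participants who have started study medication to date have permanently stopped it, or have left the study, because of adverse effects of amitriptyline or omeprazole.*

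If Appendix G already defines the count this way, cite it in 9.4 instead. Leave the serious-event condition and the resulting meeting as they are.

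Add no minimum number of participants. Everyone counted now would still be counted, over a denominator no larger than those enrolled, so on a running count the new rule is never less sensitive than the current one. A minimum would break this. With checks only from the 10th participant, counting every stop gives 0.335 at a 10% stop rate, below the 0.375 that the current text gives with 75% of stoppers leaving. It would also remove early triggers that the protocol now has.

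The cost is one sentence. The data come from the adverse event log, the check-in calls and the follow-up medication review, all already planned. The downside is a possible extra safety-monitor meeting: at a 10% stop rate with half leaving, the chance of one rises from 0.25 to 0.50, and many of these would rest on one early stop.
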